**Table 4–1: Calculation rules for duration of AEs**

Data availability	Onset date/time	Outcome date/time	Calculation rules
Complete data	D1/T1	D2/T2	$\text{Duration} = [(D2 - D1) * 24 + (T2 - T1)] / 24 \text{ d}$
End time missing	D1/T1	D2/--	End time is substituted by time 23:59h (=23.98 in decimal format) $\text{Duration} = <[(D2 - D1) * 24 + (23.98 - T1)] / 24 \text{ d}$
Start time missing	D1/-	D2/T2	Onset time is substituted by time 00:00h. $\text{Duration} = <[(D2 - D1) * 24 + T2] / 24 \text{ d}$
Start and end time missing	D1/--	D2/--	$\text{Duration} = <D2 - D1 + 1$
Start day and time missing	--/--	D2/T2	$\text{Duration} = <[(D2 - D0) * 24 + (T2 - T0)] / 24 \text{ d}$ For a participant in the SS, D0 and T0 are the date and time of first administration of UCB7665 and for screen failures, D0 is the date of the screening visit and T0 = 00:00h

**Table 4–1: Calculation rules for duration of AEs**

Data availability	Onset date/time	Outcome date/time	Calculation rules
End day and time missing	D1/T1	--/--	
For ongoing AE:
 
Duration = <math>></math>Discharge day – D1 d OR
 
Duration = <math>></math>Data cut-off day – D1 d
 
For resolved AE:
 
Duration = <math><</math>Discharge day – D1 d OR
 
Duration = <math><</math> Data cut-off day – D1 d
 
Where discharge refers to the date of the end of study visit for completed participants or the date of discontinuation for participants that were withdrawn.
 
For any AEs with known start date/time after the date of discontinuation, the date of last contact will be used as the discharge day.
 
For participants still ongoing in the study at the time of the data cut-off, and for whom no discharge date is available, the date of the data cut-off will be used instead of the discharge date.

Start and end date missing	--/--	--/--	
For ongoing AE:
 
Duration = <math>></math>Discharge day – D0 d OR
 
Duration = <math>></math>Data cut-off day – D0 d
 
For resolved AE:
 
Duration = <math><</math>Discharge day – D0 d OR
 
Duration = <math><</math> Data cut-off day – D0 d
 
For a participant in the SS, D0 and T0 are the date and time of first administration of UCB7665 and for screen failures, D0 is the date of the screening visit and T0 = 00:00h.
 
Discharge refers to the date of the end of study visit or the date of discontinuation for participants that were withdrawn.
 
For any AEs with known start date/time after the date of discontinuation, the date of last contact will be used as the discharge day.
 
For participants still ongoing in the study at the time of the data cut-off, and for whom no discharge date is available, the date of the data cut-off will be used instead of the discharge date.

D0/1/2=Date0/1/2; T0/1/2=Time0/1/2; d=day.

#### 4.2.8 Handling of repeated and unscheduled measurements

All repeated and unscheduled measurements will be presented in the listings, where applicable. The following general rules will apply to all repeated and unscheduled measurements:

- For repeated or unscheduled measurements obtained prior to dosing the latest value (which may be scheduled or unscheduled) will be used in the calculation of the descriptive statistics at each visit (ie, Screening and/or Baseline);
- For repeated or unscheduled measurements obtained at the designated Baseline visit, the latest value (which may be scheduled or unscheduled) will be defined as the Baseline provided that the measurement occurred prior to dosing;
- For repeated or unscheduled measurements taken at any timepoint after dosing, the original values (if non-missing) will be used in the calculation of changes from Baseline and for the descriptive statistics (ie, in summaries by timepoint). Unscheduled and repeated measurements will generally not be included in the summaries by timepoint after dosing.

The above rules also apply to triplicate measurements obtained for the ECG data

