## 12.2.1 Evaluation of PDILI

The PDILI IMP discontinuation criteria for this study are provided in Section 6.4.1, with the accompanying required follow-up investigation and monitoring detailed below. All PDILI events must be reported as an AE and reported to the study site and sponsor within 24 hours of learning of their occurrence. Any PDILI event that meets the criterion for potential Hy's Law must be reported as an AE of special interest, and, if applicable, also reported as an SAE (see Section 12.1.1.2).

Evaluation of PDILI consists of the diagnostic testing and continued monitoring included in Table 12-4 (specific tests dependent on laboratory results and corresponding symptoms) and consultation with a local hepatologist (if applicable; discussed in Section 12.2.1.1). The local hepatologist is the expert usually consulted by the treating physician for assessment and management of potential hepatic disease. This would usually be a hepatologist, but may be a gastroenterologist. Additional investigation and monitoring may be required and adapted based on the diagnosis after the cause of the liver injury/abnormality is confirmed (details in Section 12.2.1.4).

The results of all monitoring, including laboratory testing and other testing, should be made available to the study site and sponsor.

All initial tests resulting in abnormal hepatic laboratory values need to be repeated, but appropriate medical action must not be delayed waiting for the repeat result.

If tests are done locally for more rapid results, a concurrent sample should also be sent to the central laboratory whenever possible. Medical care decisions are to be made initially using the most rapidly available results and a conservative approach must be taken if the results from the 2 laboratory tests are significantly different. Data from the local and central laboratory are to be recorded on the applicable eCRF pages.

When IMP is discontinued, all concomitant medications and herbal supplements that are not medically necessary should also be discontinued. In these cases, the investigator should also consider dose reduction for medically necessary concomitant medication and consider changing any medically required concomitant medication known to be hepatotoxic to a suitable alternative.

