#### 10.4.2      **Electrocardiograms**

Standard 12-lead ECG recordings will be taken in triplicate with the participant resting in the supine position for at least 15 minutes and before obtaining any blood samples for assessments of laboratory variables. The following variables will be reported:

- Heart rate
- RR interval
- PQ/PR interval
- QRS duration
- QT interval
- QT corrected for heart rate using Fridericia's formula ( $QTcF = QT/(RR^{1/3})$ )

The individual measurements and the mean of the triplicate measurements will be reported in the by-participant listings. The listing will also include the change from Baseline (based on the mean of the triplicate measurements at each timepoint) and will be presented by treatment group and timepoint. The listing will also include a flag for values identified as MA/PCS as defined by the following criteria.

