**Table 10–3: MA/PCS criteria for Electrocardiograms**

Parameter	Abnormality Criteria
QT interval (ms)	>=500ms
	>=60ms increase from Baseline
QTc(F) (ms)	>=500ms
	>=60ms increase from Baseline
PR interval (ms)	Treatment-emergent value >200ms
QRS interval (ms)	Treatment-emergent value >100ms
Heart rate (bpm)	<50bpm
	>120bpm

Measured values and changes from Baseline will be summarized by treatment group at each timepoint and by ECG variable (based on the mean of the triplicate values at each timepoint).

Summarization will be as treated, participants who missed treatments will not be summarized.

The following cut-points in QTcF (raw data and change from Baseline) will be summarized categorically by treatment group (number and percentage of participants) and visit/timepoint. The denominator for the percentages will be the number of participants with a non-missing measurement for the variable at the specific visit/timepoint.

Raw QTcF data:

- <450msec
- $\geq$ 450msec to <480msec
- $\geq$ 480msec to <500msec
- $\geq$ 500msec

Change from Baseline QTcF:

- <30msec
- $\geq$ 30ms to <60msec
- $\geq$ 60msec

Electrocardiogram findings for the individual triplicate measurements will be listed separately.

Repeated and unscheduled measurements will be handled as described in Section 4.2.8.

In the event that the complete set of triplicate measurements is not available at a specified timepoint the data will be handled as described in Section 4.2.6.

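### A QTcF threshold crossing seen only at an unscheduled or repeat ECG is listed and flagged, but not counted in the QTcF category table

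*SAP*

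**What the plan says.** SAP 4.2.8 sets one general rule for repeat and unscheduled results.

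- **Listings:** "All repeated and unscheduled measurements will be presented in the listings, where applicable".
- **Before dosing:** the latest value is used, and it can become Baseline.
- **After dosing:** "the original values (if non-missing) will be used in the calculation of changes from Baseline and for the descriptive statistics". The section then adds: "Unscheduled and repeated measurements will generally not be included in the summaries by timepoint after dosing".
- **ECGs:** "The above rules also apply to triplicate measurements obtained for the ECG data".

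SAP 10.4.2 defines the QTcF cut-points, the highest being 500 msec for the raw value and 60 msec for the rise from Baseline. The counts "will be summarized categorically by treatment group (number and percentage of participants) and visit/timepoint". The denominator is the number of participants with a measurement at that visit. The same section states: "Repeated and unscheduled measurements will be handled as described in Section 4.2.8". For individual values: "The listing will also include a flag for values identified as MA/PCS as defined by the following criteria". The QTcF criteria for that flag in SAP Table 10-3 use the same two limits.

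No row or table in SAP 10.4.2 counts participants with a crossing at any time after dosing.

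**The concern.** Leaving extra measurements out is sensible for means and changes by visit. It keeps one value per participant per visit, and it stops participants who are measured more often from weighing more.

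A threshold table has a different purpose: it shows how many participants in each arm ever reached a value that matters. An ECG outside the schedule may be taken because something prompted it, and Protocol 8.5 allows unscheduled visits for safety reasons. If that ECG holds the only crossing, the table by arm shows nothing for that participant. The reader must find the case in a listing and make the comparison by hand. In a trial of this size, that can be the difference between an arm with no case and an arm with one.

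**Working it through.** The documents state no figure to reproduce. The check sets the rules side by side and then works out the weight of one participant.

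**Step 1. When scheduled ECGs occur (Protocol 8.2.3, 8.2.5, 8.2.7, 8.3.1 and 8.3.2).** After the first dose they fall at Visits 4, 6, 8, 10, 12, 14, 16, 17 and 21, that is, Days 8, 15, 22, 36, 50, 64, 78, 85 and 162.
- From Visit 8 to Visit 16 the spacing is 36 − 22 = 14 days, and the same for each later pair.
- From Visit 17 to Visit 21 it is 162 − 85 = 77 days.
- Stabilization visits (Protocol 8.3.3) include no ECG.

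An ECG taken inside one of these gaps has no column of its own in a table by scheduled visit.

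**Step 2. Applying SAP 4.2.8 and 10.4.2 to each situation.**
- *The scheduled ECG crosses and the repeat is normal.* The original value is kept, so the participant is counted.
- *The scheduled ECG does not cross but the repeat does.* The original value is used. The repeat is listed and flagged, and not counted.
- *Only an unscheduled ECG crosses.* It is listed and flagged, and not counted.
- *Both a scheduled and an unscheduled ECG cross.* The participant is counted at the scheduled visit.
- *The scheduled value is missing and an extra one exists.* The text is unclear. The condition that the original be non-missing suggests that the extra value might stand in.
- *The ECG is taken at the premature end of treatment (PEOT) visit.* SAP 4.3 maps it to a scheduled visit, so it is counted.

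The gap is therefore confined to the second and third situations, and possibly part of the fifth.

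**Step 3. Weight of one uncounted participant.** Protocol 5.1.2 and SAP 2.4 plan 34 randomized participants, 1:1.
- 34 / 2 = 17 per arm, and 1 / 17 = 5.9 percentage points.
- With the 15 per group used for power in SAP 2.4, 1 / 15 = 6.7 percentage points.

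This is the weight of one participant, not an estimate of how many would be missed. The documents give no rate of unscheduled ECGs or of QTcF crossings, so that number cannot be derived.

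**The case against.** The best case for leaving the plan as it is has four parts.

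- **Nothing is lost.** Every extra ECG is listed and marked abnormal values are flagged. With 34 participants, each can be read individually. This is true, and it limits the consequence. It does not supply a count by arm.
- **The protocol is satisfied.** Protocol 14.4.1 asks only for categorical QTc analyses, and a by-visit table is one. This also stands: the point is a weakness of the table, not a departure from the protocol.
- **The rule is softened.** SAP 4.2.8 speaks of what is generally done, so an exception is possible. None is stated for QTcF, and SAP 10.4.2 refers to the rule without qualification.
- **The rule can protect a signal.** An abnormal scheduled value is not replaced by a normal repeat. This is correct. A reader might infer that the rule removes the worst values first and biases safety counts towards no finding. The documents do not support that as a general statement. A value is lost from the counts only when the threshold is crossed at the extra ECG alone, and the frequency of that is unknown.

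A reader might also infer that liver signals are dropped in the same way, because Protocol 12.2.1 says: "All initial tests resulting in abnormal hepatic laboratory values need to be repeated". Table 12-4 also asks for liver monitoring at least twice a week in most PDILI categories, unless another schedule is agreed. The text does not show such a loss:

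- The exclusion in SAP 4.2.8 concerns summaries by timepoint. The PDILI table in SAP 10.3.1 is a separate count of participants who meet a criterion at any visit.
- SAP 10.4.1 and 10.4.2 cite 4.2.8, while 10.3 and 10.3.1 do not.
- The PDILI symptom criteria are matched by date within two days, not by scheduled visit.
- PDILI events must also be reported as adverse events (Protocol 12.2.1) and potential Hy's Law cases as adverse events of special interest (Protocol 12.1.1.3). SAP 10.2 tabulates both kinds.

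A figure for how many liver results would be unscheduled therefore says nothing about a loss from the counts.

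**Conclusion.** The point holds for QTcF and is small. On the text of SAP 4.2.8 and 10.4.2, a participant whose only crossing of 500 msec, or of a 60 msec rise, is at an unscheduled or repeat ECG is flagged in the listing and left out of the QTcF table. Such a participant would enter a table by arm only if the event were separately recorded as an adverse event, and the documents contain no requirement to do so for QTcF.

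One such participant is 5.9 percentage points of an arm of 17. This rests on equal arms of the planned size and on reading the general rule as applying in full to QTcF, as the cross-reference indicates. The number of participants affected could be zero.

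For the liver table there is no demonstrated error. What remains is a possible difference in how two programmers read it, which a few words would settle.

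**What to change.** Keep the SAP 4.2.8 exclusion for by-timepoint means, changes from Baseline and by-visit category counts. Add to the QTcF category table in SAP 10.4.2 one participant-level row by treatment group for the worst post-dose value. Apply it to the raw value and to the rise from Baseline, using all post-dose ECGs: scheduled, unscheduled and repeat. State the row's denominator as participants with at least one post-dose ECG, and add a sentence in 4.2.8 naming this row as an exception.

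Optionally, state in SAP 10.3.1 that repeat and unscheduled liver results count towards the PDILI criteria.

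The cost is SAP wording and one table row, with no new data. The downside is that participants with more ECGs have more chances to cross a threshold. A footnote giving the number of post-dose ECGs per arm would let the reader judge that.

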#### **4.3 Handling of measurements obtained at the premature end of treatment visit**

Participants who withdraw from the study prematurely will be encouraged to return for the PEOT visit. The following rules will apply with regard to the inclusion of the results obtained at the PEOT in the descriptive summaries:

- Any measurements (including efficacy, safety, immunological and PD assessments) conducted at the PEOT should be included in the summaries for the respective scheduled visit, if the PEOT occurs at the time of the next scheduled visit (within the tolerance window specified in the protocol).
- If the PEOT does not correspond to the day of a scheduled visit, the efficacy, safety and other relevant assessments of the PEOT should be mapped to the nearest scheduled visit, relative to the Baseline visit date, following the last scheduled visit where assessments are available.
- If the date of the PEOT is equidistant between 2 scheduled visits at which no scheduled assessments were performed, the assessments from the PEOT will be mapped to the earliest of these visits.

Different domains from the same PEOT may be re-assigned to different study visits depending on the study schedule of assessments ie, measurements obtained at the PEOT can only be mapped to a scheduled visit at which the respective assessment was intended to be measured. Assessments from the PEOT that are mapped to scheduled visits will be flagged in the data listings.

Visits after the PEOT following the schedule of the 12-Weeks Observation period, will be mapped to the corresponding planned visit. Assessments on these visits will be flagged in the data listing.

#### **4.4 Interim analyses and data monitoring**

A Data Monitoring Committee (DMC) will be established to monitor mainly safety data during the study. The efficacy data will be assessed during the third interim analysis. The interim analyses will be unblinded and thus the live randomization code will be utilized in the datasets and TFLs.

Details about the Interim analyses will be provided in a separate DMC SAP.

#### **4.4.1 Timing of interim analyses**

The following interim analyses are performed:

- The first interim analysis will be conducted after 8 participants have received their first 4 subcutaneous (sc) infusions and have attended the next visit (Visit 9). Based on this unblinded analysis the PK, PD and safety of rozanolixizumab will be assessed by the DMC
- The second interim analysis will be conducted after 8 participants (receiving 12 sc infusions) have attended the first visit of the Observation Period (ie, Visit 17, the visit 1 week after last dosing). Based on this unblinded analysis the PK, PD and safety of rozanolixizumab will be assessed by the DMC
- The third interim analysis will take place after data from 8 additional participants are available, ie, after 16 participants have attended the first visit of the Observation Period. Based on this unblinded analysis the PK, PD and safety of rozanolixizumab will be assessed by the DMC
  - Following DMC recommendations from the second interim analysis, listings and descriptive summary statistics for iRODS, INCAT and site personnel reported grip strength will be included in the third interim analysis
- A fourth interim analysis was planned, but will not be performed. Please see Section 3.9.2 for details.

If needed, subsequent DMC meetings will take place. The timing of further interim analyses and reviews of the data by the DMC will be decided by the DMC. Ad hoc DMC meetings can be held for reasons determined appropriate by the sponsor.

#### **4.4.2 Data required for interim analyses**

The analyses and data required for review are described in the DMC SAP and include all data specified in the DMC Charter.

#### **4.5 Multicenter studies**

Individual center results will not be displayed.

#### **4.6 Multiple comparisons/multiplicity**

Not applicable.

#### **4.7 Use of an efficacy subset of participants**

Not applicable.

#### **4.8 Active-control studies intended to show equivalence**

Not applicable.

#### **4.9 Examination of subgroups**

Not applicable.

### **5 STUDY POPULATION CHARACTERISTICS**

#### **5.1 Participant disposition**

The number of participants who were enrolled, dosed, participants included in each analysis set, and participants who completed or prematurely discontinued the study, as well as the

reason for discontinuation, discontinuation due to AEs, will be presented by treatment group and overall. Screen failure reasons will be summarized, based on the ES.

In addition, the following listings will be presented by treatment group:

- Participant disposition (ES)
- Study discontinuation (ES)
- Visit dates (RS)
- Participant analysis sets (ES)

Participant disposition will be listed by treatment group based on the ES, and will include the date of informed consent, date of randomization, date and time of first and last dose of IMP, date of premature termination and primary reason, and date of final contact (if applicable).

The listing of study discontinuation will include the reason for discontinuation, period of discontinuation, with dose and number of days on that dose and the total number of days on study medication.

The number of days on IMP will be calculated as follows:

Number of days on IMP=(Date of Last Dose Received)-(Date of First Dose Received)+1

Time to discontinuation will be listed and plotted in a Kaplan-Meier-Curve for all discontinuations versus discontinuation due to COVID-19.

Reasons for screening failures, disposition and discontinuation reasons will also be summarized based on the respective event's date relative to the COVID-19 period.

## **5.2 Protocol deviations**

Important protocol deviations (IPDs) will be identified and classified by the deviation types identified in the IPD document. A listing of all IPDs identified at the Data evaluation meetings (DEMs) will be presented for all participants in the RS, and will include the deviation type and description. The number and percentage of participants in the RS with IPDs will be summarized overall if appropriate. The denominator for percentages will be the number of participants in the RS.

A separate listing will present the captured data from the "COVID-19 Impact" eCRF form. Frequencies of impact categories by visit will also be presented for each relatedness category (suspected, confirmed, general or other reasons). Important protocol deviations will be summarized by COVID-19 period and relationship to COVID-19 (any, related, not related). Number and percentage of participants with these protocol deviations will be summarized for the RS.

Start of the pandemic will be the date the WHO recognized COVID-19 as pandemic, 20 March 2020. The cut-off date for the post- subgroup level will be defined prior to database lock if applicable, an update to the pre-COVID-19 cut-off date may be performed. Details of the analyses will be specified in the following sections.

A date is considered pre COVID-19 up to the day before the start date, so 19 March 2020.

## **6 DEMOGRAPHICS AND OTHER BASELINE CHARACTERISTICS**

## 6.1 Demographics

A by-participant listing of Baseline demographics will be presented by treatment group for the ES. This will include the year of birth (if available), age (in years), gender, race, ethnicity, height (in cm), weight (in kg) and body mass index (BMI), region and country. The age will be directly entered into the study database and will not be re-calculated for the statistical analysis.

Childbearing potential will be listed for the ES.

All demographic characteristics, except date of birth, obtained at the Screening visit will be summarized for the RS.

Body mass index in  $\text{kg}/\text{m}^2$  is calculated based on the height (in m) and the weight (in kg) measured at the Screening visit using the following formula:

$$\text{BMI } (\text{kg}/\text{m}^2) = \text{weight } (\text{kg}) / [\text{height } (\text{m})]^2$$

The BMI will be reported to 1 decimal place.

Age will be classified into categories based on requirements for European Union Drug Regulating Authorities Clinical Trials (EudraCT) and clinicaltrials.gov reporting.

For the EudraCT reporting, the age categories will include

- 18 to <65 years
- 65 to <85 years
- $\geq 85$  years

For the clinicaltrials.gov reporting, the age categories will include:

- $\leq 18$  years
- 19 to <65 years
- $\geq 65$  years

Body weight at screening will be summarized in the following categories:

- <50 kg
- 50 to <70 kg
- 70 to  $\leq 100$  kg
- $\geq 100$  kg

